6.9 Excluded Treatments and/or Procedures During Study Period

Use of any over-the-counter or prescription medications within the 14 days or 5 half-lives (whichever is longer), prior to receiving the first dose of AMG 334 or PACAP-38. Simple

analgesics including NSAIDs will be allowed, but not within 48 hours prior to infusion of PACAP38. Subjects are not allowed to be on preventive therapies for migraine.

Paracetamol (up to 2 g per day) for analgesia and hormone replacement therapy (eg, estrogen, thyroid) will be allowed. Simple analgesics including NSAIDs will be allowed, but not within 48 hours prior infusion of PACAP-38. Subjects are allowed to take rescue medication for a migraine attack (their usual migraine treatment or a triptan) and for adverse events, such as emesis and allergic reactions (clemastin 2 mg, prednisolone 100 mg). Any herbal medicines (eg, St. John's wort), vitamins, and supplements consumed by the subject within 21 days prior to receiving the first dose of AMG 334, and continuing use if applicable, will be reviewed by the investigator and the Amgen Medical Monitor. Written documentation of this review and Amgen acknowledgement are required for subject participation. Refer to Section 6.5 for guidance on concomitant therapy.

- 7. STUDY PROCEDURES
- 7.1 Schedule of Assessments

Activity	Screeni	ng	Treatment Period											Fo	EOS Visit					
Study Day	-21 to -2	-1	Day 1 ^a						Dav	Day 9	Day 10	Day 29	Day 57	85						
Time (in hours)			Pre- Dose	0	0.5	1	Pre- Dose	0	0.25	0.5	1	2	3	4	8	24	48			
General & Safety Assessments	F	1	1	1	1		1				٩	I	1		1	I	٩	٩		
Informed Consent	Х						h													
Residency							X	Х	Х	Х	Х	Х	Х	Х	Х	Х				
Medical History	X																			
Body Weight	X	Х																		Х
Height	Х						~			~		~				~				
Vital Signs (BP, HR, RR, TEMP) ^g	X	Х	Х		Х	Х	X ^g		Х	X g	Х	Xg	Х	Х	Х	Xg	Х	Х	Х	Х
Physical Examination	Х	Х																Х		Х
Neurological Examination	Х		Х				Х									Х		Х		Х
12-lead Electrocardiogram ^c	X		Х		Х		Х			Х	Х	Х		Х	Х	Х	Х			Х
Adverse Event Recording				Х	Х	Х	Х	Х	Х	Х	Х	Х	Х	Х	Х	Х	Х	Х	Х	Х
Serious Adverse Event	Х	Х	Х	Х	Х	Х	Х	Х	Х	Х	Х	Х	Х	Х	Х	Х	Х	Х	Х	Х
Concomitant Medications	Х	Х	Х	Х	Х	Х	Х	Х	Х	Х	Х	Х	Х	Х	Х	Х	Х	Х	Х	Х
Laboratory Assessments	-											-								
Creatinine Clearance ⁱ	Х	х					х									Х				
Clinical Chemistry	Х	Х					Х									Х				Х
Clinical Hematology	Х	Х					Х									Х				Х
Urinalysis '	Х	Х					Х									Х				Х
Drug, Alcohol & Cotinine Screen	Х	Xj					X ^{h j}													
HIV, HepCAb, HBsAg, HBcAb	Х																			
Postmenopausal status test, (females only) ^k	Х																			
Cardiac Enzymes	Х	Х					Х					Х		Х	Х	Х				
Pregnancy Test (females only) ^d	Х	Х					Х													Х
Questionnaires																				
Headache Questionnaire		Х						Х	Х	Х	Х	Х	Х	Х	Х	Х				
Columbia-Suicide Severity Rating Scale	Х	Х	х				х									Х		Х	Х	Х

Table 2. Schedule of Assessments For Part B: Randomized (AMG 334 or Placebo) Subjects

Footnotes are defined on the next page of table

Page 1 of 2

Activity	Screeni	Treatment Period											Fo	EOS Visit						
Study Day	-21 to -2	-1		Day 1 ^ª				Day 8 ^{b f g}										Day 29	Day 57	85
Time (in hours)			Pre- Dose	0	0.5	1	Pre- Dose	0	0.25	0.5	1	2	3	4	8	24	48			
Dosing																				
Study Drug Administration				Х																
Challenge-agent (PACAP-38) ^f								X ^f												
Pharmacokinetic and Other Blood	Samples																			
Antibody Sample Collection			Х															Х	Х	Х
AMG 334 Serum PK Collection ^e			Х			Х	Х			X e								Х	Х	Х
CGRP Plasma Collection			Х				Х		Х	Х										Х
PACAP-38 Plasma Collection							Х		Х	Х										
Cell Pellet for Pharmacogenetics			Х																	

Table 2. Schedule of Assessments For Part B: Randomized (AMG 334 or Placebo) Subjects

Page 2 of 2

Abbreviations: ECG = electrocardiogram; EOS = end of study; FSH = follicle-stimulating hormone; HepBsAg = hepatitis B surface antigen; HepCAb = hepatitis C antibody; HBcAB = hepatitis B core antibody; HIV = human immunodeficiency virus; PK = pharmacokinetic

^{a.} Subjects will return to the research facility one day prior to investigational product administration (Day -1), at which time baseline procedures will be completed. After completion of all pre-dose and baseline laboratory and vital sign procedures on the day of dosing (Day 1), subjects will receive AMG 334 or matching placebo. -Subjects will reside at the research facility for at least 1 hour and then be discharged home.

^{b.} Subjects will return to the research facility on Day 8, at which time pre-dose procedures will be completed. After completion of pre-dose procedures on Day 8, subjects will receive PACAP-38. Subjects will reside at the research facility for at least 24 hours post PACAP-38 infusion and then be discharged home.

^{c.} At Screening ECGs will be performed in a standardized method, in triplicate, and approximately 30 seconds apart, prior to blood draws or other invasive procedures. Single ECGs will be performed from Day 1 to EOS.

^{d.} A serum pregnancy test will be performed at screening. Serum or highly sensitive urine (cutoff of 20 mlU/L) pregnancy tests will be performed at Day -1, Day 8 Pre-Dose and EOS.

^{e.} Flexible PK sampling point, that could be collected at any time on Day 8 between pre-PACAP-38 to 2 hours post-PACAP-38 administration.

^{f.} PACAP-38 should not be administered if subject reports having a headache within 72 hours prior to Day 8. Subject should return to the research facility from Day 8 – Day 12 for PACAP-38 administration.

⁹ Rectal temperature will be collected after obtaining blood pressure, prior to PACAP-38 infusion and post PACAP-38 infusion at Hours 0.5, 2 and 24.

^{h.} Negative drug, alcohol and cotinine test is required prior to PACAP-38 dose. Positive results will be reviewed between the PI and MM on a case by case basis.

¹ Laboratory results required prior to AMG 334 and PACAP-38 dose. Abnormal lab results will be reviewed between the PI and MM on a case by case basis prior to PACAP-38 dose.

^{j.} A reliable urine drug test performed at the site is allowed.

^k Additional serum will be collected for an FSH, LH, or estradiol test for postmenopausal women at screening as defined in Section 7.2.22.

¹ Cardiac enzymes include CPK-MB and Troponin I or Troponin T.

	0		The first of Parts I					Follo	w-Up	EOS				
Activity	Screenin	ng										Per		VISIT
Study Day	-21 to -2	-1										Day 2	Day 3	Day 8
Time (in nours)			Pre-Dose	0	0.25	0.5	1	2	3	4	ð	24	48	
General & Safety Assessments	X	1	1			-	1	1		1			 	
Informed Consent	X				X		V	V	V	V	X			
Residency		-	X	X	X	X	Х	Х	Х	Х	Х	X		
Medical History	X													
Body Weight	X	X												X
Height	X		a a d					a d				d		
Vital Signs (BP, HR, RR, TEMP) ^u	Х	Х	Xu		Х	Χu	Х	Xu	Х	Х	Х	Χu	Х	Х
Physical Examination	Х	Х												Х
Neurological Examination	Х		Х									Х		Х
12-lead Electrocardiogram ^a	Х		Х			Х	Х	Х		Х	Х	Х	Х	Х
Adverse Event Recording				Х	Х	Х	Х	Х	Х	Х	Х	Х	Х	Х
Serious Adverse Event	Х	Х	Х	Х	Х	Х	Х	Х	Х	Х	Х	Х	Х	Х
Concomitant Medications	Х	Х	Х	Х	Х	Х	Х	Х	Х	Х	Х	Х	Х	Х
Laboratory Assessments														
Creatinine Clearance	Х	Х										Х		
Clinical Chemistry	Х	Х										Х		Х
Clinical Hematology	Х	Х										Х		Х
Urinalysis	Х	Х										Х		Х
Drug, Alcohol & Cotinine Screen	Х	Xe												
HIV, HepCAb, HBsAg, HbcAb	Х													
Postmenopausal status test (females only) [†]	Х													
Pregnancy Test (females only) ^b	Х	Х												Х
Cardiac Enzymes ^g	Х	Х	Х					Х		Х	Х	Х		
Questionnaires														
Headache Questionnaire		Х		Х	Х	Х	Х	Х	Х	Х	Х	Х		
Columbia-Suicide Severity Rating Scale	Х	Х	Х									Х		Х
Dosing														
Challenge-agent (PACAP-38) ^c		1		Xc										
Pharmacokinetic and Other Blood Samples	5													
CGRP Plasma Collection			X		X	Х								X
PACAP-38 Plasma Collection			Х		Х	Х	İ							
Cell Pellet for Pharmacogenetics			Х											

Table 3. Schedule of Assessments Part A: For Non Randomized (PACAP-38 Only) Dose Selection Subjects

Footnotes are defined on the next page of table

Product: AMG 334 Protocol Number: 20140207 Date: 01 September 2016

Abbreviations: ECG = electrocardiogram; EOS = end of study; FSH = follicle-stimulating hormone; HepBsAg = hepatitis B surface antigen; HepCAb = hepatitis C antibody; HBcAB = hepatitis B core antibody; HIV = human immunodeficiency virus; PK = pharmacokinetic;

^{a.} At Screening ECGs will be performed in a standardized method, in triplicate, and approximately 30 seconds apart, prior to blood draws or other invasive procedures.-Single ECGs will be performed from Day 1 to EOS.

^b A serum pregnancy test will be performed at screening. Serum or highly sensitive urine (cutoff of 20 mIU/L) pregnancy tests will be performed at Day -1 and EOS.

^{c.} PACAP-38 should not be administered if subject reports having a headache within 72 hours prior Day 1. Subject should return to the research facility from Day 1 – Day 5 for PACAP-38 administration.

^{d.} Rectal temperature will be collected after obtaining blood pressure, prior to PACAP-38 infusion and post PACAP-38 infusion at Hours 0.5, 2 and 24.

^{e.} A reliable urine drug test performed at the site is allowed.

^{f.} Additional serum will be collected for an FSH, LH or estradiol test for screening for postmenopausal women as defined in Section 7.2.22.

^{g.} Cardiac enzymes include CPK-MB and Troponin I or Troponin T.

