On Day 1, approximately 2 subjects in Cohort 1 will receive an infusion of 10 pmol/kg/min over 2.5 minutes (total dose 25 pmol/kg). The PI will be responsible to review heart rate (HR) and blood pressure (BP). The BP assessment is based on a single measurement of systolic blood pressure (SBP) of >150 mm Hg or diastolic blood pressure (DBP) > 100 mm Hg. If the mean heart rate increase of the subjects in Cohort 1 is greater than 50% over baseline during a 2 hour period after dosing and SBP does not increase to >150 mm Hg or DBP to >100 mm Hg, then approximately 3 subjects in Cohort 2 will receive an infusion of 10 pmol/kg/min over 5 minutes (total dose 50 pmol/kg). Written documentation from Amgen of the decision to proceed with enrollment in Cohort 2 is required. After dosing Cohort 2 and any subsequent cohort, the PI will again be responsible to review HR and BP using previously outlined criteria. These same criteria shall also be assessed for Cohort 3.

After dosing Cohort 3, up to 5 subjects in Cohort 4 will receive 10 pmol/kg/min over 10 minutes (total dose 100 pmol/kg). Following Cohort 4, a Dose-Level-Review Meeting (DLRM) will occur to decide the dose of PACAP-38 to be used in the randomized portion of the study (Part B). This decision will be primarily based on safety and tolerability data,

and number of subjects experiencing a headache and/or MLA in Cohort 4, although all of the available data for Cohorts 1 to 4 will be reviewed. The dose- selection for Part B will be based on the goal of ensuring subject safety and ideally triggering headache in all subjects within a given cohort and moderate to severe MLAs in the majority of subjects within the same cohort. However, the trigger of headaches in the majority of subjects within a given cohort and mild, moderate or severe MLAs in the majority of subjects within the same cohort may be considered acceptable to advance to the randomized portion of the study (Part B). If this goal is not achieved, following the DLRM review of the Cohort 4 data, then Cohort 5 dosing of 10pmol/kg/ min over 11.5 minutes (total dose 115 pmol/kg) can commence.

Cohorts 2, 3 and 4 enrollment will occur after a Safety Review Meeting between the principal investigator (PI), medical monitor (MM), and global safety officer (GSO) or designee. At that time, available vital signs and adverse events occurring at least 24 hours following PACAP-38 dosing will be reviewed.

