If the PI, MM, and GSO or designee decide not to proceed with enrollment into a subsequent cohort, then a Safety Review Meeting or DLRM will be held after the last dosed cohort. Refer to Section 10.4.2 for additional information on the Safety Review Meetings and DLRMs. The Safety Review Meeting or DLRM voting members will decide whether or not to proceed with enrollment in Part B Randomization (AMG 334 or Placebo) Phase and if the decision is made to proceed, the Safety Review or DLRM voting members will select the appropriate PACAP-38 dose. The decision to proceed with Part B of the study will be based on the goal of ensuring subject safety and ideally triggering headache in all subjects within a given cohort and moderate to severe MLAs in the majority of subjects within a given cohort and mild, moderate or severe MLAs in the majority of subjects within the same cohort may be considered acceptable to advance to Part B of the study.

All available study data, including the headache questionnaires, demographics, investigational product administration, medical history, concomitant medications, adverse events (including MLA), ECGs, vital signs, and laboratory results will be reviewed. Data to be reviewed at the DLRMs during the PACAP-38 Dose Selection Phase will not be blinded. Data to be reviewed for any unscheduled DLRM post the PACAP-38 Dose Selection Phase will be reviewed blinded (ie, treatment assignment will not be revealed) unless unblinding is deemed necessary for the review team to make

dosing decisions. If deemed necessary, unblinding will be performed to assist dose decisions in accordance with Amgen standard procedures.

6.3.1.3 PACAP-38 - Dosage Adjustments, Delays, Rules for Withholding, or Restarting Stopping or Permanent Discontinuation

Dosing of PACAP-38 will be stopped or modified by the DLRM voting members if suspected unexpected treatment related adverse events of Grade 2 or greater in the same system organ class occur in 2 or more subjects or Grade 3 occur in 1 or more subject. Dosing of PACAP-38 will also be stopped or modified by the DLRM voting members under the following circumstances:

- a) Blood pressure:
 - a. Systolic BP > 150 mm Hg OR
 - b. Diastolic BP > 100 mm Hg OR
 - c. Decrease in SBP from baseline > 30 mm Hg OR
 - Decrease in DBP from baseline > 15 mm Hg and considered clinically relevant after consultation between the investigator and the medical monitor.

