Any changes in blood pressure as defined above must be confirmed with 3 consecutive measurements taken approximately 5 minutes apart and with the subject remaining in a semi-recumbent position. The mean of the 3 measurements will be the final recorded value.

- b) Mean heart rate increase of subjects in a given cohort is greater than 50% or greater than 20% decrease over baseline during a 2 hour period after dosing
- c) Changes in other vital signs or clinical laboratory results considered to pose a significant health risk to subjects

In addition, any clinically or medically significant suspected adverse drug reactions and serious adverse events considered to be related to study procedures will be followed until resolved or considered stable.

The study may be terminated at any point in time at the discretion of the sponsor.

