7.2 General Study Procedures

Any blood sample collected according to the Schedule of Assessments (Table 2 and Table 3) may be analyzed for any of the tests outlined in the protocol and for any tests necessary to ensure subject safety. This includes testing to ensure analytical methods produce reliable and valid data throughout the course of the study. This may also include, but is not limited to, investigation of unexpected results, incurred sample reanalysis, and analyses for method transfer and comparability.

Throughout the study, the permitted time windows for scheduled assessments will be as follows:

- +4 day for Day 1 For Non Randomized (PACAP-38 Only) Dose Selection Subjects Only
- + 4 day for Day 8 for Randomized (AMG 334 or Placebo) Subjects
- ± 30 minutes for Headache Questionnaire
- ± 3 days for Days 29, Day 57 and EOS (Day 8 for Non Randomized (PACAP-38 Only) Dose Selection Subjects and Day 85 for Randomized (AMG 334 or Placebo) Subjects)

If informed consent is provided by the subject, Amgen may do additional testing on remaining samples (ie, residual and back-up) to investigate and better understand neurological disorders, the dose response and/or prediction of response to AMG 334, characterize antibody response, and characterize aspects of the molecule. Results from this analysis will be documented and maintained, but may not be reported as part of this study.

Additional procedures deemed necessary as part of standard of care or as required by local laws and regulations may be performed at the Investigator's discretion.

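### Tables 2 (Day 8) and 3 schedule no HR/BP assessment between pre-dose and 0.25 h and leave hour 0 undefined; one end-of-infusion assessment would narrow the gap at little cost

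*Protocol*

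**What the plan says.** Protocol 7.1 sets the assessment times. In Table 3 (Part A) and Table 2 (Part B, Day 8) the row "Vital Signs (BP, HR, RR, TEMP" is marked at pre-dose, empty at hour 0, and then marked at 0.25, 0.5, 1 and 2 h and later. The hour 0 column itself is in use: adverse-event recording and the PACAP-38 infusion are both marked there. The first post-dose ECG is at 0.5 h.

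Protocol 7.2 states that "the permitted time windows for scheduled assessments will be as follows". The list that follows has no entry for vital signs.

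Two sets of limits use the readings:

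- **Protocol 6.3.1.2 (Part A escalation).** "The BP assessment is based on a single measurement", against upper limits of 150 mm Hg systolic and 100 mm Hg diastolic. The review carries on through Part A: "After dosing Cohort 2 and any subsequent cohort, the PI will again be responsible to review HR and BP using previously outlined criteria".
- **Protocol 6.3.1.3 (stopping or modifying PACAP-38).** It uses the same upper limits and adds limits on falls, among them "Decrease in DBP from baseline > 15 mm Hg and considered clinically relevant". A BP change "must be confirmed with 3 consecutive measurements taken approximately 5 minutes apart", and "The mean of the 3 measurements will be the final recorded value". A separate heart-rate item applies when "Mean heart rate increase of subjects in a given cohort is greater than 50" per cent over a 2 h period.

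Protocol 3.1 gives the PACAP-38 half-life as 3.5 min. Section 2.4 expects short-lived rises in heart rate and blood pressure. The Amendment 3 rationale reports, from Part A so far, a transient rise in heart rate and a fall in diastolic pressure.

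**The concern.** The challenge agent is short-lived and acts on the circulation. Its plasma level should be highest at the end of the infusion, and no HR/BP measurement is required then. The first required reading comes minutes later, and how many minutes depends on a time origin that the protocol does not fix. The tables mark the infusion itself at hour 0, which suggests the start. The rectal-temperature footnotes count their hours from after the infusion, which suggests the end. Two sites could therefore take the same nominal reading at different times relative to the dose.

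At stake is whether a brief BP change is recorded at all. A change that has resolved by 0.25 h, and that nobody happens to measure, can neither count in the single-measurement check of 6.3.1.2 nor trigger the confirmation in 6.3.1.3. An unscheduled value would also be left out of the HR and BP summaries over time planned in SAP 10.6.2.2, because SAP 10.1 builds such summaries from scheduled time points. It would still count in the minimum and maximum changes.

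**Working it through.** **Inputs.** Infusion rate 10 pmol/kg/min and durations T = 2.5, 5, 7.5, 10 and 11.5 min (Protocol 2.4 and 6.3.1.1); half-life 3.5 min (Protocol 3.1); first post-dose vital signs at 0.25 h = 15 min (Tables 2 and 3).

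**1. The plan's own doses.** Rate × T = 10 × 2.5, 5, 7.5, 10, 11.5 = 25, 50, 75, 100 and 115 pmol/kg, as stated.

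**2. The schedule rows.** Each vital-signs row was matched cell by cell to its time header: 20 cells in Table 2 and 14 in Table 3. Hour 0 is blank in both. The cells carrying the rectal-temperature footnote fall at pre-dose and at 0.5, 2 and 24 h, as that footnote says, so the alignment is sound.

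**3. Time from end of infusion to the first scheduled reading.** If hour 0 is the start, the gap is 15 − T. As a rough guide to exposure, assuming constant-rate input and first-order elimination, the fraction of the end-of-infusion level left is 2^(−gap/3.5).

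| Dose (pmol/kg) | T (min) | Gap = 15 − T (min) | Half-lives = gap/3.5 | Level left |
|---|---|---|---|---|
| 25 | 2.5 | 12.5 | 3.6 | 8% |
| 50 | 5 | 10 | 2.9 | 14% |
| 75 | 7.5 | 7.5 | 2.1 | 23% |
| 100 | 10 | 5 | 1.4 | 37% |
| 115 | 11.5 | 3.5 | 1.0 | 50% |

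If hour 0 is the end, the gap is 15 min at every dose: 15/3.5 = 4.3 half-lives, about 5% left. On either definition no scheduled HR/BP time falls during or at the end of an infusion. At a given dose the two definitions differ by T, so by up to 11.5 min.

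**4. Readings available to the 2 h heart-rate rule.** These are at 0.25, 0.5, 1 and 2 h, so four; one more makes five. The rule uses a cohort mean, so the addition changes little.

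**5. Overlap caused by a confirmation.** Three readings about 5 min apart span 2 × 5 = 10 min. With hour 0 as the start, and the end-of-infusion reading counted as the first of the three, a series at 100 pmol/kg runs from 10 to 20 min and one at 115 pmol/kg from 11.5 to 21.5 min. Both span the 0.25 h vital signs and the 0.25 h CGRP and PACAP-38 blood draws.

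**6. Reach.** Section 2.4 and the Amendment 3 rationale give 2 + 3 + 2 + 4 = 11 Part A subjects dosed, against a cap of 25, so at most 25 − 11 = 14 remain. Amendment 3 thinks it more likely that one lower-dose cohort will be expanded. Filling it to 5 adds 5 − 3 = 2 subjects at 50 pmol/kg, or 5 − 2 = 3 at 25 or 75 pmol/kg. Part B, as printed, has up to 36 randomised subjects.

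**The case against.** The infusion period is not ignored. Section 2.4 has subjects under close observation during the infusion, 6.3.1 requires a physician to be present, infusion start and stop times are recorded, and 7.2.10 has every measurement that is taken recorded. The instruction manual for PACAP-38 administration is outside these documents and may specify monitoring. A reader might infer that subjects go unmonitored during the infusion; the documents say otherwise. What stands is that none of these provisions, so far as can be seen, requires an HR/BP measurement at a stated time.

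Nor is there evidence of a loss. The documents give no time course for HR or BP, plasma level is only a proxy, the existing readings did pick up transient effects, and Amendment 3 reports that no subject met the stopping criteria. A reader might infer that peaks or stopping events were missed; nothing supports that.

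A reader might also expect an earlier reading to bring an earlier decision. It would not. Action under 6.3.1.3 belongs to the dose-level review members, and enrolment of Cohorts 2 to 4 rests on a meeting that reviews data from at least 24 h after dosing. By the end of infusion the full dose has been given.

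Further points against are fair. A very brief change may be averaged away in the three-reading mean. The BP limits in 6.3.1.2 are upper limits only, while the direction reported so far is a diastolic fall, so the decrease limits in 6.3.1.3 are the more relevant ones. If hour 0 is the start, the gap is shortest at the highest doses. These lower the priority but do not remove the point.

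**Conclusion.** The point holds as an inexpensive improvement to safety monitoring, of low priority. As printed, neither schedule requires an HR/BP reading from pre-dose until 3.5 to 12.5 min after the end of infusion (hour 0 as start) or 15 min after it (hour 0 as end), and hour 0 is undefined. A short-lived BP change could go unrecorded against the limits in 6.3.1.2 and 6.3.1.3. The size of any missed change is unknown and may be nil. The heart-rate rule is barely affected, and the efficacy endpoints are not affected.

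It would be too much to say that one added reading closes the gap: up to 11.5 min of infusion would still have no scheduled reading.

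The conclusion rests on the tables in the 01 September 2016 protocol. The SAP follows Amendment 4 of 21 October 2016, whose schedules are not available here. It therefore applies to remaining Part A subjects and to Part B only if those schedules do not already include such a reading.

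**What to change.** In Table 2 (Day 8) and Table 3, add one HR/BP assessment at end of infusion, with BP taken as 7.2.10 describes (semi-recumbent). In one footnote:

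- define hour 0 as the start or the end of the PACAP-38 infusion;
- state that the new assessment counts toward 6.3.1.2 (Part A cohorts) and 6.3.1.3;
- keep the three-reading BP confirmation as it is.

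If the Amendment 4 schedules already contain such a reading, no new assessment is needed.

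The cost is a few minutes per infusion in an in-house, attended subject. It is slightly more than a single cuff reading, because 7.2.10 asks for at least two BP measurements, averaged. Section 6.3.1.1 asks for a supine position for about an hour after PACAP-38, so the footnote should make clear that the position in 7.2.10 governs this assessment. The downside is a few more out-of-range values to confirm, possibly overlapping the 0.25 h assessments and blood draws.
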